10.7 Interim analysis

There is no interim analysis planned.

10.8 Withdrawals and deviations

All withdrawn subjects will be listed individually, including at least subject number, date and reason for withdrawal, and last visit performed.

Subjects with protocol deviations will be listed individually, including subject number and observed deviation. Depending on the seriousness of the deviation, subject might be excluded from the PP population, which shall be documented prior to database lock.

Deviations from the statistical plan will be documented.

10.9 Sample size

[REDACTED]

[REDACTED]

[REDACTED]

[REDACTED]

[REDACTED]

[REDACTED]

[REDACTED]

11. Protection of personal data

All processing of personal data must be carried out in accordance with national legislation concerning the protection of personal data. The Institution and the Investigator are responsible for complying with all requirements pursuant to national legislation in which the Institution and the Investigator are located. The Sponsor will ensure that all requirements for data processing are fulfilled.

The Investigator understands that clinical studies conducted under an IDE are exempt from the study subject identifier confidentiality provisions of the Health Insurance Portability and Accountability Act of 1996 (HIPAA), and the study subject should be made aware of this exception in the informed consent. The Institution and Investigator are jointly responsible for providing sufficient information to all subjects to enable them to give their informed consent not only to the participation in the investigation, but also to the processing of Personal Data. Such information includes information regarding the purposes of the processing, the length of time during which Personal Data will be stored, the right of access to stored Personal Data and the right to correction or purging of incorrect or obsolete Personal Data. A subject may also withdraw his or her consent at any time.

A subject who withdraws his or her consent to the processing of Personal Data must be considered to have withdrawn from the investigation but the data collected until the consent was withdrawn may be used in the statistical analyses.

Authorized representatives from the Sponsor or a RA may visit the investigational site to perform audits/inspections, including source data verification, i.e., comparing data in the subjects' medical records and the eCRF. Data and information will be handled with strict confidentiality.

12. Quality Control and Quality Assurance

12.1 Quality control

On-site monitoring of the study will be arranged by the Sponsor according to GCP guidelines to verify that the rights and well-being of the subjects are protected, the reported data are accurate, complete, verifiable from source documents, and that the conduct of the study complies with the approved CIP, subsequent amendment(s), GCP and the applicable regulatory requirements.

Any CIP deviation shall be reported in the eCRF, which will be verified, discussed, and collected by the monitor and appropriate actions will be taken. The Investigator is responsible for promptly reporting any deviations from the CIP that affects the rights, safety or well-being of the subject or the scientific integrity of the study, including those which occur under emergency circumstances, to the Sponsor as well as the IRB if required by national regulations. Deviations will be reviewed to determine the need to amend the CIP or to terminate the study. Handling of CIP deviations will be performed as described in the monitoring manual.

12.2 Quality assurance

The study site may be subject to quality assurance audit by the Sponsor as well as inspection by appropriate RA. It is important that the Investigator and other relevant study site personnel are available during the monitoring visits, possible audits, and inspections, and that sufficient time is devoted to the monitoring process.

Each participating member of the study site team shall provide a curriculum vitae (CV) or equivalent that demonstrates their qualifications to conduct the study.

It is the responsibility of the Investigator to ensure that all personnel involved in the study are fully informed of all relevant aspects of the study, including detailed knowledge of and training in all procedures to be followed. All Investigators and other responsible persons shall be listed together with their function in the study on a signature and delegation log.

12.3 Changes to the clinical study protocol

The Investigator and other site personnel involved in the study must not implement any deviation from or changes to the CIP without agreement with the Sponsor and prior review and documented approval from the IRB, except where necessary to eliminate an immediate hazard to the subjects. All changes to the final CIP must be documented in a written protocol amendment. However, administrative changes are to be documented in the Sponsor file without requiring a protocol amendment. The Sponsor will assess if the changes require prior FDA approval, and inform the Investigator when such approval has been received.

13. Financing, Indemnification, and Insurance

The CTA outlines the compensation and payment terms of the study. The CTA must be signed before the first subject is screened in the study. If there are differences between the CTA and the CIP regarding certain rights and obligations, the CTA is the prevailing document.

The Sponsor's obligations in this clinical study are covered by Galderma's global general liability program. An insurance certificate will be provided upon request. The Institution/Investigator is obligated to maintain insurance coverage for their obligations in the clinical study according to the CTA.

14. Publication Policy

The Investigator's, Institution's, and Sponsor's obligations regarding intellectual property rights, confidentiality, and publications are described in detail in the CTA.

This study will be displayed on clinicaltrials.gov in accordance with local regulations. The aim is to submit the results of this study for publication. Everyone who is to be listed as an author of the publication shall have made a substantial, direct, intellectual contribution to the work. Authorship will be based on (1) substantial contributions to the conception or design of the work; or the acquisition, analysis, or interpretation of data for the work; and (2) drafting the work or revising it critically for important intellectual content; and (3) final approval of the version to be published; and (4) agreement to be accountable for all aspects of the work in ensuring that questions related to the accuracy or integrity of any

## 1 Study Information

### 1.1 Background

#### 1.1.1 Study design

This is a randomized, controlled, evaluator-blinded, multi-center study to evaluate the effectiveness and safety of *Restylane® Kysse* for lip augmentation and correction of perioral rhytids.

Approximately 280 subjects will be randomized in a 2:1 ratio of treatment to control and treated. Approximately 187 subjects will be treated with *Restylane® Kysse* and 93 subjects will receive the control in the lips and perioral rhytids and will be followed for 48-weeks.

[REDACTED]

Investigator blinding will be accomplished by using a Treating Investigator to administer the treatments and a Blinded Evaluator, to whom randomization and treatment are concealed, to conduct the blinded assessments.

Safety assessments will be performed by non-blinded personnel. Eligible subjects randomized to receive treatment will be injected by the Treating Investigator at Day 1.

#### 1.1.2 Number of subjects and randomization

Approximately 280 subjects will be randomized to treatment or to control in a 2:1 ratio (treatment: control) stratified by FST (I-III, IV or V-VI) to achieve a total sample size of 234 evaluable subjects

[REDACTED]

Before starting the study, a randomization list will be prepared under the supervision of a designated statistician. Randomization will be performed using an Interactive Response System by assigning each subject to *Restylane® Kysse* or the control according to the randomization list.

### 1.2 Study objectives

#### 1.2.1 Primary efficacy objective

The primary objective of the study is to demonstrate non-inferiority of *Restylane® Kysse* versus a control in lip fullness augmentation by comparing change from baseline [REDACTED] in the upper and lower lip separately, at 8 weeks after last injection.

#### 1.2.2 Secondary efficacy objectives

- To evaluate the effectiveness of *Restylane® Kysse* in lip fullness augmentation [REDACTED]

- To evaluate the aesthetic improvement of the upper perioral rhytids and oral commissures after treatment with Restylane® Kysse, [REDACTED]
- To evaluate the aesthetic improvement (overall appearance) after treatment *Restylane® Kysse*, [REDACTED]
- Subjects' satisfaction after treatment with *Restylane® Kysse* [REDACTED]
- Lip fullness compared to baseline, [REDACTED]

#### 1.2.3 Safety objectives

- To evaluate all AEs at all visits and pre-defined, expected, post-treatment events reported during the first 4 weeks after treatment as recorded in the subject diary.
- To evaluate the safety assessment at all visits, as assessed by a qualified staff member:
  - [REDACTED]
  - [REDACTED]
  - [REDACTED]

#### 1.2.4 Exploratory objectives

- To evaluate the consistency of the primary analysis results across different subgroups, specifically:
  - Study site
  - Fitzpatrick skin types (I-III and IV-VI)
  - Race
- To evaluate the consistency of AE data across different subgroups, specifically:
  - Study site
  - Injection volume
  - Fitzpatrick skin types (I-III and IV-VI)
- [REDACTED]

### 1.3 Efficacy assessments

Day 1 is defined as the date of initial treatment.

For all assessments, baseline is defined as the last observation before initial treatment takes place at the baseline visit on Day 1. Change from baseline is defined as the post-baseline value minus the baseline value.

### 1.3.1

Version: 2.0

*Effective*

Version: 2.0

## *Effective*

Version: 2.0

### 1.3.5

1. **What is the primary purpose of the proposed legislation?**

## 1.4 Efficacy endpoints

### 1.4.1 Primary efficacy endpoint

The primary end point is change from baseline [REDACTED]

[REDACTED] at 8 weeks after last injection of *Restylane® Kysse* or control treatment.

[figure not shown]
### 1.4.2 Secondary efficacy endpoints

The secondary efficacy endpoints will include the following:

(i) [REDACTED]

(iv) [REDACTED]

[REDACTED]

## 1.5 Safety assessments

The methods for collecting safety data are described in Section 8 of the Clinical Study Protocol (CSP) and includes the following: assessment of adverse events (AEs) by direct question to subject and evaluation of subject, as well as pre-defined, expected, post-treatment events reported in the subject diaries; [REDACTED]

[REDACTED] laboratory assessments (urine pregnancy test only); and device deficiencies.

Each AE, serious as well as non-serious, shall be assessed by the Investigator for causal relationship with the study product and its use (the injection procedure) and for seriousness (Yes or No) of the event.

A two-point scale (Yes or No response) shall be used for the causality assessments. The Investigators shall be asked to indicate a response to each of the following questions in the eCRF:

- “Do you consider that there is a reasonable possibility that the event may have been caused by the study product?”, and
- “Do you consider that there is a reasonable possibility that the event may have been caused by the device injection procedure?”

If any of these questions is answered with a ‘Yes’, the AE will be considered related. Each AE will also be assessed for causal relationship and seriousness by the Sponsor, in order to fulfil regulatory requirements. In case of disagreement, the AE will be classified as “Related”.

## 1.6 Safety endpoints

Safety endpoints include:

## 2 Statistical Methods

### 2.1 General methods

All statistical analyses, including summary tables and data listings, will be performed using the SAS® system (Version 9.3 or higher). Confidence intervals (CIs) will be two-tailed and constructed at a confidence level of 95%. P values will be two-sided and performed at a significance level of 5%.

All study data including observed and derived variables (e.g., change from baseline, response status) used in the summaries of analyses will be presented in by-subject listings. In general, efficacy, safety, demography, subject characteristics, and treatment related variables will be presented using descriptive statistics. For categorical parameters, the number and percentage of subjects in each category will be presented. The denominator for percentage will be based on the number of observations at that time point (i.e. observed cases). For continuous parameters, descriptive statistics will include number of observations, mean, standard deviation (SD), median, and range. Graphs will be used as appropriate.

Any change made to the finalized statistical analysis plan (SAP) after database lock will be documented in the Clinical Study Report (CSR).

For the primary analysis, non-inferiority will only be demonstrated if the CI is entirely below 0.5 for both co-primary endpoints in both the ITT and PP populations. Similarly, superiority will only be demonstrated if the lower confidence limit is entirely below 0 for both co-primary endpoints in both the ITT and PP populations. Therefore no multiplicity adjustment for Type I error is required.

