### 2.4.3 Primary efficacy analysis

Non-inferiority will be established if the CI is entirely below 0.5 for both co-primary endpoints in both the ITT and PP populations. Superiority will be declared if the CI is entirely below 0 for both co-primary endpoints in both the ITT and PP populations. This decision criteria is consistent with a gate-keeping strategy (testing for superiority following the test for non-inferiority) to maintain the overall type I error rate at 5%.

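### SAP 2.1 ties superiority to the lower confidence limit being below 0, while SAP 2.4.3 requires the whole CI below 0 for the same co-primary endpoints

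*SAP*

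**What the plan says.** The SAP states the success criteria for the co-primary endpoints (change from baseline at Week 8, upper and lower lip separately) in two places.

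- **Non-inferiority.** SAP 2.1: "non-inferiority will only be demonstrated if the CI is entirely below 0.5 for both co-primary endpoints". SAP 2.4.3: "Non-inferiority will be established if the CI is entirely below 0.5 for both co-primary endpoints". Both require this in ITT and PP, so the two sections agree.
- **Superiority.** SAP 2.1: "superiority will only be demonstrated if the lower confidence limit is entirely below 0 for both co-primary endpoints". SAP 2.4.3: "Superiority will be declared if the CI is entirely below 0 for both co-primary endpoints in both the ITT and PP populations". Both again cover ITT and PP, but they name different parts of the interval.

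SAP 2.1 sets two-sided 95% intervals and a two-sided 5% significance level. Directly after its two rules it concludes that no multiplicity adjustment is needed. SAP 2.4.3 says that its criteria, with superiority tested after non-inferiority, keep the overall type I error rate at 5%.

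**The concern.** A lower limit below 0 shows only that the data do not establish Kysse as worse than control. It is not evidence that Kysse is better. With the difference oriented so that a CI below 0.5 means non-inferiority, superiority requires the upper limit to be below 0, as 2.4.3 has it.

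The sentence in 2.1 is introduced as applying to the primary analysis and has the same form as the non-inferiority criterion before it, so it reads as a decision rule. No visible text says which section prevails. If 2.1 were programmed or quoted literally, superiority could be claimed from an interval that contains 0, and the 5% error rate stated in 2.4.3 would not hold for that step. The study is meant to support a US marketing application (protocol 2.3), and a correction made after results are known would look outcome-driven.

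**Working it through.** **Inputs from the documents**
- Two-sided 95% CI (SAP 2.1), so z = 1.96.
- Non-inferiority margin 0.5 (SAP 2.1 and 2.4.3).
- 234 evaluable subjects, 2:1 allocation (SAP 1.1.2): 234 × 2/3 = 156 Kysse and 78 control.
- Approximately 187 Kysse and 93 control subjects treated (SAP 1.1.1), used for ITT.

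**Assumptions**
- The SD is not visible, so 0.7 to 1.2 is used. Between-lip correlation is taken as 0 to 0.9.
- Lower differences favour Kysse, as the form of the non-inferiority rule implies.
- Normal approximation, complete data, no imputation. The true difference is 0 in both lips.

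**1. An interval on which the sections disagree.** Take a CI of (-0.20, +0.30) for both lips.
- Non-inferiority: 0.30 < 0.5, met.
- Superiority under literal 2.1: -0.20 < 0, met.
- Superiority under 2.4.3: 0.30 is not below 0, not met.

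The half-width is 0.25, so SE = 0.25/1.96 = 0.1276. At 156:78 that corresponds to an SD of about 0.92.

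**2. The plan's own 5% figure, under 2.4.3.** Per endpoint, P(upper limit < 0) = Φ(-1.96) = 2.5%, the favourable half of a two-sided 5% test. For both endpoints together this is 0.0006 (0.06%) at correlation 0, 0.0046 at 0.5 and 0.015 at 0.9. The stated error control is reproduced: the rate never exceeds 2.5%.

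**3. The literal 2.1 condition, one population.** Per endpoint, P(lower limit < 0) = Φ(+1.96) = 97.5%. For both endpoints this is 0.975² = 95.1% at correlation 0, rising to 96.5% at 0.9. It does not depend on SD or sample size.

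**4. Adding the non-inferiority gate, one population.** SE = SD × √(1/156 + 1/78) = 0.1387 × SD. Passing both steps requires each estimate to be below min(1.96·SE, 0.5 − 1.96·SE). The gate matters only when SE > 0.5/3.92 = 0.1276, that is, SD above about 0.92.

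Worked case, SD 1.0, correlation 0: 0.5 − 1.96 × 0.1387 = 0.228; 0.228/0.1387 = 1.646; Φ(1.646)² = 0.950² = 90.3%.

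**5. Gate plus both populations.** 400,000 simulated trials per setting, with PP (156:78) nested in ITT (187:93) and all four intervals required to pass.

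| SD | Literal 2.1 + gate, one population | Literal 2.1 + gate, ITT and PP |
|---|---|---|
| 0.7 to 0.9 | 95.1% to 96.5% | 93.2% to 95.3% |
| 1.0 | 90.3% to 93.2% | 89.5% to 92.7% |
| 1.1 | 82.1% to 87.7% | 80.8% to 86.8% |
| 1.2 | 72.6% to 81.1% | 70.6% to 79.6% |

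Ranges run over correlation 0 to 0.9. Under the 2.4.3 rule, requiring both ITT and PP gives 0.02% to 0.9%.

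**The case against.** The strongest defence is that 2.1 says superiority is shown only if the lower limit is below 0, which strictly is a necessary condition. Any interval entirely below 0 also has its lower limit below 0, so a result that passes 2.4.3 always satisfies 2.1. On that reading 2.1 is redundant, and following 2.4.3 satisfies both sections. In addition, 2.4.3 is the dedicated primary-analysis section, the wording in 2.1 suggests that an interval was meant, and 2.1's own two-sided 5% level would not call an interval containing 0 significant. A trial statistician is unlikely to program the lower limit.

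Much of this stands: it supports a drafting slip and makes the practical risk modest. It does not rescue the sentence. The non-inferiority rule just before it has the same only-if form and plainly serves as the criterion, and 2.1 presents the superiority rule as its parallel. The statement that no multiplicity adjustment is needed follows from both rules. Even as a necessary condition, 2.1 names the wrong limit and excludes almost nothing.

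It is also fair that the 95% figure is a property of any lower 95% limit under no difference, and that the gated figures rest on assumed SDs and correlations and ignore the hot deck imputation in protocol 10.6. The example interval makes the point without them.

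**Conclusion.** The inconsistency is real and lies in complete, current text of both sections. The 2.1 superiority criterion is wrong as written; 2.4.3 already holds the valid rule. Read literally and with non-inferiority required first, 2.1 would allow a superiority claim in about 71% to 95% of trials with no true difference (ITT and PP both required, SD 0.7 to 1.2, correlation 0 to 0.9), against under 1% for 2.4.3 on the same basis. The exact percentages depend on the assumptions listed; the direction does not.

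The reach is limited. Non-inferiority, the stated primary objective, has the same rule in both sections, and the sample size is not affected. Only the follow-on superiority claim is exposed. This should be fixed, but it does not undermine the design.

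**What to change.** Before database lock, reword the superiority sentence in SAP 2.1 so that it requires the CI to lie entirely below 0 (upper limit of the two-sided 95% CI below 0) for both co-primary endpoints in both ITT and PP, matching 2.4.3. Alternatively, delete the duplicate rules from 2.1 and refer to 2.4.3, leaving one statement of the criteria. The cost is one line of SAP wording, with no effect on data collection, sample size or the non-inferiority test.

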### 2.2 Analysis Populations

The following populations will be defined for analysis:

- **Safety population:** Includes all subjects who received any of the investigational products, based on the as treated principle (i.e. according to the treatment actually received).
- **Intention-to-treat (ITT) population:** Includes all subjects who were randomized [REDACTED] All ITT analyses will be based on the as randomized principle (i.e. according to the treatment they were randomized to).
- **Per protocol (PP) population:** Includes all subjects in ITT who complete the Week 8 visit without any deviations considered to have substantial impact on the primary effectiveness outcome.

The primary efficacy analysis of non-inferiority will be performed both on the ITT and the PP analysis set. Secondary effectiveness and all safety evaluations will be performed based on the ITT and the safety population set, respectively.

### 2.3 Study subjects

#### 2.3.1 Subject disposition

The number of subjects in each study population (i.e. Safety, ITT and PP) will be summarized. Study population variables will also be presented in a data listing.

The disposition of subjects will be presented by treatment group, and in total, including numbers of subjects that were:

- Screened
- Randomized
- Completed
- Withdrawn (overall and by reason for withdrawal)

All withdrawn subjects will be presented in a by-subject listing.

### 2.3.2 Protocol deviations

Protocol deviations will be presented in a by-subject listing. Major protocol deviations will be summarized by site and overall.

Depending on the seriousness of the deviation, subject might be excluded from the PP population, which shall be documented prior to database lock.

For this study, the protocol deviations that will exclude subjects from PP are identified (but not limited to) below:

- General
  - Treatment not given according to randomization scheme at initial or touch-up (if touch-up done) treatment
- Efficacy
  - Pre-treatment value missing for at least one lip
  - Any other deviation considered to have substantial impact on the primary effectiveness outcome
- Other
  - Any key inclusion/exclusion criteria not met ( [REDACTED] )
    - Use of any prohibited medications or procedures defined in study protocol between initial treatment and the Week 8 visit, that is considered to have a substantial impact on the primary effectiveness outcome

Deviations from the SAP will be documented in the CSR.

### 2.3.3 Demographic characteristics

Demographic endpoints, baseline assessments, and subject characteristics will be summarized overall and by treatment for the ITT populations.

The following demographic and baseline variables will be included:

- Age (years)
- Sex
- Race
- Ethnicity

- Fitzpatrick skin types (FST)
- [REDACTED]
- [REDACTED]

